12.2.3. Relationship to Investigational Product

The investigator must make the determination of relationship to the IP for each adverse event (not related, related). The following definitions should be considered when evaluating the relationship of AEs and SAEs to the IP.

| Not Related | An AE will be considered "not related" to the use of the IP if there is not a reasonable possibility that the event has been caused by the IP. Factors pointing towards this assessment include but are not limited to: the lack of temporal relationship between administration of the IP and the event, the presence of biologically implausible relationship between the product and the AE, or the presence of a more likely alternative explanation for the AE. |
|-------------|---|
| Related | An AE will be considered "related" to the use of the IP if there is a reasonable possibility that the event may have been caused by the product under investigation. Factors that point towards this assessment include but are not limited to: a positive rechallenge, a reasonable temporal sequence between administration of the drug and the event, a known response pattern of the suspected drug, improvement following discontinuation or dose reduction, a biologically plausible relationship between the drug and the AE, or a lack of alternative explanation for the AE. |

12.2.4. Recording Adverse Events

Adverse events spontaneously reported by the participant and/or in response to an open question from the study personnel or revealed by observation will be recorded during the study at the investigational site. The AE term should be reported in standard medical terminology when possible. For each AE, the investigator will evaluate and report the onset (date and time), resolution (date and time), intensity, causality, action taken, outcome and seriousness (if applicable), and whether or not it caused the participant to discontinue the IP or withdraw early from the study.

Intensity will be assessed according to the following scale:

- Mild: symptom(s) barely noticeable to participant or does not make participant uncomfortable; does not influence performance or functioning; prescription drug not ordinarily needed for relief of symptom(s)
- Moderate: symptom(s) of a sufficient severity to make participant uncomfortable;
 performance of daily activity is influenced; participant is able to continue in study;
 treatment for symptom(s) may be needed
- Severe: symptom(s) cause severe discomfort; symptoms cause incapacitation or significant impact on participant's daily life; severity may cause cessation of treatment with IP; treatment for symptom(s) may be given and/or participant hospitalized

It is important to distinguish between serious and severe AEs. Severity is a measure of intensity whereas seriousness is defined by the criteria in Section 12.2.2. An AE of severe intensity may not necessarily be considered serious.

12.2.5. Reporting Serious Adverse Events

In order to adhere to all applicable laws and regulations for reporting an SAE(s), the study site must notify Sage or designee within 24 hours of the study site staff becoming aware of the SAE(s). The investigator must complete, sign and date the SAE report form, verify the accuracy of the information recorded on the SAE report form with the corresponding source documents, and send a copy to Sage or designee.

Additional follow-up information, if required or available, should all be sent to Sage or designee within 24 hours of receipt on a follow-up SAE report form and placed with the original SAE information and kept with the appropriate section of the eCRF and/or study file.

Serious adverse events occurring after the designated follow-up time for the study, should be reported to Sage or designee according to the timelines noted above only if the investigator considers the SAE related to IP.

Sage, or designee, is responsible for notifying the relevant regulatory authorities of certain events. It is the principal investigator's responsibility to notify the IRB/IEC of all SAEs that occur at his or her site. Investigators will also be notified of all suspected unexpected serious adverse reactions (SUSARs) that occur during the clinical study. IRBs/IECs will be notified of SAEs and/or SUSARs as required by local law.

Sage, or designee, will submit SUSARs (in blinded or unblinded fashion) to regulatory agencies according to local law and investigators.

12.3. Pregnancy

If a participant becomes pregnant after the first administration of IP, pregnancy information must be collected and recorded on the Pregnancy form and submitted to the sponsor within 24 hours of learning of the pregnancy. Details will be collected for all pregnancies for which conception was likely to have occurred after the start of IP administration until 5 terminal half-lives following the last administration of IP or until the completion of the study whichever is longer. Any pregnancy occurring in that time frame will be followed until delivery or termination of the pregnancy. The investigator will also attempt to collect pregnancy information on any participant's partner who becomes pregnant after the participant has received the first administration of IP. After obtaining the necessary signed informed consent from the pregnant partner directly, the investigator will follow the same pregnancy reporting procedures specified for pregnant participants.

The participant or participant's partner will be followed to determine the outcome of the pregnancy. The outcome of all pregnancies (eg, spontaneous abortion, elective abortion, normal birth) must be followed and documented even if the participant was discontinued from the study. The investigator will collect follow-up information on the participant or participant's partner and the neonate, and the information will be forwarded to Sage or designee. Generally, follow-up will not be required for longer than 6 to 8 weeks beyond the estimated delivery date. Any termination of pregnancy will be reported, regardless of fetal status (presence or absence of anomalies) or indication for the procedure.

Pregnancy in itself is not regarded as an AE unless there is a suspicion that an IP may have interfered with the effectiveness of a contraceptive medication. Any complication during pregnancy (eg, anemia, infections, preeclampsia) should be reported as an AE/SAE. If the outcome of the pregnancy meets the criteria for immediate classification as an SAE (ie, spontaneous abortion, stillbirth, neonatal death,), the investigator should follow the procedures for reporting an SAE.

12.4. Overdose

An overdose is any dose of study treatment given to a participant or taken by a participant that exceeds the dose described in protocol. Overdoses are not considered AEs and should not be recorded as an AE on the eCRF; however, all overdoses must be recorded on an overdose form and sent to Sage or designee within 24 hours of the site becoming aware of the overdose. An overdose must be reported to Sage or designee even if the overdose does not result in an AE. If an overdose results in an AE, the AE must be recorded.

13. STATISTICS

Detailed description of the analyses to be performed in the study will be provided in the statistical analysis plan (SAP). The SAP will be finalized and approved prior to database lock. Any changes/additions to the SAP following database lock will be described in detail in the clinical study report.

13.1. Data Analysis Sets

The Safety Set will include all participants who were administered IP and will be used to describe the safety data.

13.2. Handling of Missing Data

Every attempt will be made to avoid missing data. All participants will be used in the analyses, as per the analysis populations, using all nonmissing data available. No imputation process will be used to estimate missing data.

13.3. General Considerations

All participant data, including those that are derived, that support the tables and figures will be presented in participant data listings.

For the purpose of all primary and secondary analyses where applicable, baseline is defined as the last measurement prior to the first dose of IP.

Continuous endpoints will be summarized with number (n), mean, standard deviation, median, minimum, maximum, Q1, and Q3. In addition, change from baseline values will be calculated at each time point and summarized descriptively. For categorical endpoints, descriptive summaries will include counts and percentages.

13.4. Demographics and Baseline Characteristics

Demographic data, such as age, sex, race, and ethnicity, and baseline characteristics, such as height, weight, and body mass index, will be summarized using the Safety Set.

Pregnancy test results and alcohol and drug test results will be listed but not summarized.

Medical history, MRI results, and amyloid-PET results will be listed by participant.

13.6. Safety Analyses

Safety and tolerability of SAGE-718 will be evaluated by TEAEs and change from baseline in vital signs, clinical laboratory analytes, ECGs, and responses on the C-SSRS. Safety data will be listed by participant and summarized by treatment group. All safety summaries will be performed on the Safety Set.

13.6.1. Adverse Events

AEs will be coded using Medical Dictionary for Regulatory Activities version 22.0 or higher. A TEAE is defined as an AE with onset after the first dose of IP. The analysis of AEs will be based on the concept of TEAEs. The incidence of TEAEs will be summarized by System Organ Class and preferred term. In addition, summaries will be provided by intensity (mild, moderate, severe) and by causality (related, not related) to IP.

Any TEAEs leading to discontinuation or interruption of treatment or withdrawal from the study and any treatment-emergent SAEs will be summarized.

All AEs and SAEs (including those with onset or worsening before the start of IP) through the end of the study will be listed.

13.6.2. Clinical Laboratory Evaluations

Results of clinical laboratory parameters in each scheduled visit and mean changes from baseline will be summarized in standard units. Normal ranges for each parameter will be provided by the laboratory; shift from baseline to postbaseline values in abnormality of results will be provided. Potentially clinically significant values will be summarized by treatment. Clinical laboratory results will be listed by participant and timing of collection.

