12.1.7. Laboratory Assessments

Blood and urine samples for clinical laboratory assessments will be collected. will be collected for hematology, biochemistry, coagulation, urinalysis, and serology at the time points detailed in Table 2 and Table 3.

During Screening only, samples for clinical laboratory assessments will be collected from participants when they are in a fasted state.

Analytes to be evaluated are summarized in Table 4.

Table 4: Summary of Clinical Laboratory Analytes

| Biochemistry | Renal Panel: glucose, calcium, phosphorus, blood urea nitrogen, creatinine, sodium, potassium, chloride, bicarbonate |
|--------------|---|
| | Hepatic Panel: albumin, ALT, AST, total bilirubin, direct bilirubin, indirect bilirubin, alkaline phosphatase, total protein, lactate dehydrogenase, gamma glutamyl transferase |
| | Other: triglycerides, cholesterol (LDL, HDL), creatine phosphokinase, thyroid stimulating hormone |

| Coagulation | activated partial thromboplastin time, prothrombin time, and international normalized ratio |
|------------------------------|---|
| Hematology | red blood cell count (RBC), hemoglobin, hematocrit, white blood cell count with differential, platelet count, and if RBC indices are abnormal, reflex RBC morphology is indicated |
| Urinalysis | protein, glucose, pH, blood, leukocytes, leukocyte esterase, urobilinogen, bilirubin, ketones, nitrite |
| Serology (screening only) | hepatitis B surface antigen, hepatitis C IgM antibody, HIV-1 antibody, HIV-2 antibody |

Follicle stimulating hormone testing will be conducted to confirm whether a participant with ≥12 months of spontaneous amenorrhea meets the protocol-defined criteria for being postmenopausal.

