# 6.1 Changes from the Protocol

- Protocol section 13.6.6 mentions the prior and concomitant medications will only be listed. Along
  with the listing a summary table will also be provided.
- Protocol section 13.4 mentions that Medical history will be only listed. Besides listing medical history will also be summarized.

 Alzheimer's disease history will be summarized and listed as per the data collected on the CRF page.

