### 16.2 Clinical Laboratory Evaluations

Laboratory assessments for biochemistry, coagulation, hematology, urinalysis, and serology, will be collected at screening, Day -1, Day 7, Day 14, and Day 28. The clinical laboratory tests to be performed for monitoring safety are listed in **Table 4**. Laboratory assessments will be summarized (n, mean, std,

median, Q1, Q3, minimum, and maximum) along with the change from baseline by each scheduled post-baseline visit. The International System of Unit (SI) will be used.

For the laboratory results that is "< or = x", where x is a number as collected in the data, the numeric part of the result will be used in the calculation in the summary tables. The same is true if the result is presented as below limit of quantification (BLQ) and a lower limit of quantification (LLOQ) value is provided – LLOQ value will be used for calculation in the summary tables. The actual results as collected will be displayed in the listings.

Summary tables on lab parameters will include descriptive statistics for the observed values and changes from baseline by scheduled assessment timepoint in hematology, serum chemistry, coagulation, and quantitative urinalysis test results.

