**Table 4 Clinical Laboratory Tests** 

Hematology	Serum Chemistry	Urinalysis	Coagulation
Hematology Red blood cell count Hemoglobin Hematocrit White blood cell count with differential Platelet count Red Blood Cell Indices (MCV, MCH, MCHC) Reflex to Red blood cell morphology if indices are abnormal	Serum Chemistry  Alanine aminotransferase Albumin Alkaline phosphatase Aspartate aminotransferase Total bilirubin Direct bilirubin Indirect bilirubin Total protein Creatinine Blood urea nitrogen Creatine kinase Gamma-glutamyl transferase	Urinalysis pH  Protein Glucose Red blood cell Nitrite Leukocyte esterase Ketones Bilirubin Urobilinogen	Coagulation  Activated partial Thromboplastin time Prothrombin time International normalized ratio
apnormai		Urobilinogen	
	Thyroid stimulating hormone (TSH)		

If a normal range is provided for the parameter, out-of-range values will be flagged as low or high, where applicable, in the participant data listings

The number and percentage of participants with potentially clinically significant (PCS) values will be provided in separate displays in hematology, serum chemistry, and liver function tests provided for such occurrence by time point.

PCS values will be identified for specific laboratory parameters as outlined in Table 5.

Liver function tests will be monitored closely for PCS values, and will be summarized for occurrence any time post-baseline for the following parameters for these PCS thresholds (for conditions involving more than one parameter, the results need to be from the same timepoint):

Alanine Aminotransferase: >3xULN, >5xULN, >10xULN Aspartate Aminotransferase: >3xULN, >5xULN, >10xULN

Alanine Aminotransferase or Aspartate Aminotransferase: >3xULN, >5xULN, >10xULN

Alkaline Phosphatase: >1.5xULN, >2xULN

Total Bilirubin: >1.5xULN, >2xULN

Total Bilirubin > 2xULN **AND** (Alanine Aminotransferase or Aspartate Aminotransferase >3xULN)
Total Bilirubin >2xULN **AND** Alkaline Phosphatase >2xULN **AND** (Alanine Aminotransferase or

Aspartate Aminotransferase >3xULN)

Any lab results considered clinically significant by the investigator will be captured as adverse events, hence will show up in AE displays.

Pregnancy test results will be listed but not summarized.

Table 5 Potentially Clinically Significant Values for Specific Laboratory Parameters

Laboratory Parameter	Gender	Units	Criteria for PCS Values (Observed values)		
			High	Low	
Hematology					
Hemoglobin	Male	g/L	>185	<115	
	Female	g/L	>170	<100	

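### The protocol promises laboratory shifts in abnormality, but the SAP plans none and does not declare the change; its by-time-point hematology counts may also miss abnormal unscheduled values

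*Protocol*

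**What the plan says.** **Protocol.** Section 13.6.2 plans visit results and mean changes from baseline, then refers to the laboratory's normal ranges and says "shift from baseline to postbaseline values in abnormality of results will be provided". It asks for a summary of PCS values and, in a separate sentence, for participant listings. The analytes are in protocol Table 4 (Section 12.1.7), including "Other: triglycerides, cholesterol (LDL, HDL), creatine phosphokinase, thyroid stimulating hormone".

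**SAP displays.** Section 16.2 says samples "will be collected at screening, Day -1, Day 7, Day 14, and Day 28". It then says: "Summary tables on lab parameters will include descriptive statistics for the observed values and changes from baseline by scheduled assessment timepoint". Normal ranges are used in one place: "out-of-range values will be flagged as low or high, where applicable, in the participant data listings". PCS counts, against the limits in SAP Table 5, go in "separate displays in hematology, serum chemistry, and liver function tests provided for such occurrence by time point". Liver tests have a further rule: a set of thresholds "will be summarized for occurrence any time post-baseline for the following parameters".

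**SAP table list.** Appendix F has six consecutively numbered laboratory tables, 14.3.3.1.1 to 14.3.3.3.2. They are results by time point and PCS tables. No title refers to a shift.

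**Declared changes.** SAP 6.1 lists three differences in displays from the protocol: medications, medical history and Alzheimer's disease history. A typical entry begins "Protocol section 13.4 mentions that Medical history will be only listed". None concerns laboratory shifts.

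**Record selection.** SAP 13.10 uses at most one record per participant and window in by-visit summaries. A scheduled record takes precedence over an unscheduled one, and unused records go to listings.

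**The concern.** This is a single-arm study, so each participant's own baseline is the only reference within the trial. A shift table gives the number of participants whose result was normal before dosing and out of range afterwards. Summaries of change do not give that number, because a mean change can be small while a few participants leave the normal range.

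PCS counts do not replace it either. Table 5 uses fixed limits or multiples of the upper limit of normal. Only creatinine has an option relative to baseline. A PCS count therefore does not, in general, separate a new abnormality from one already present before dosing, and it covers only analytes that have a limit.

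The second question is which records the PCS counts use. An unscheduled sample may be drawn because something looked wrong. If a by-time-point table takes only the scheduled value, that sample does not reach the count.

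**Working it through.** The plan states no figure to reproduce here. The check compares the texts, counts the analytes and applies the record-selection rule.

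**1. Is the shift display planned anywhere in the SAP?** Of the six laboratory tables in Appendix F, none is a shift display. Urinalysis categories are tabulated by time point, not against baseline. Section 16.2 describes none, and SAP 6.1 does not mention its removal.

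**2. Which blood analytes have no tabulated abnormality count?**
- Protocol Table 4: renal 9 + hepatic 10 + other 5 + coagulation 3 + hematology 5 = 32, with the white-cell count and its differential as one analyte.
- Counting the five differential cell types separately, as SAP Table 5 does: 32 + 5 = 37.
- Named parameters in SAP Table 5: hematology 9 + non-liver chemistry 12 + liver 4 = 25. This takes bilirubin there to be total bilirubin, and leaves out an unnamed row that repeats the chloride limits.
- Without a limit: 37 − 25 = 12. On the other base, the six white-cell rows collapse to one, so 20 are covered and 32 − 20 = 12 again.
- The 12 are red-cell count, direct and indirect bilirubin, LDH, triglycerides, LDL, HDL, CPK, TSH, aPTT, PT and INR.
- Red-cell count and the two bilirubin fractions overlap with covered analytes. Without them: 12 − 3 = 9.

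| Base | No limit | No limit and no covered counterpart |
|---|---|---|
| 32 | 12/32 = 38% | 9/32 = 28% |
| 37 | 12/37 = 32% | 9/37 = 24% |

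**3. Can a by-time-point PCS count miss an abnormal value?** Assume that SAP 13.10 governs the PCS tables. For a participant who completes dosing, SAP Table 1 gives three post-baseline windows: Days 2–10, Days 11–17, and Day 26 onward. There are three scheduled post-baseline draws, on Days 7, 14 and 28. With one record per window and scheduled data first, a participant with all three scheduled values contributes no unscheduled value. Days 18–25 (25 − 18 + 1 = 8 days) lie in no window.

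Illustration with assumed platelet counts (×10⁹/L; the Table 5 low limit is below 125): scheduled 180, 175 and 182, plus one unscheduled value of 110.

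| Day of unscheduled value | Window | By-time-point count | Any-time count |
|---|---|---|---|
| 9 | Day 7, scheduled value present | 0 | 1 |
| 20 | none | 0 | 1 |

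One participant is 1/22 = 4.5%, or 1/20 = 5.0% of completers. The documents give no number of unscheduled draws, so no expected loss can be calculated.

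**4. Which tables are affected?** For the 9 hematology parameters, the text of 16.2 and the title of Table 14.3.3.1.2 both say by time point. For the 12 non-liver chemistry parameters the text says so, but the title of Table 14.3.3.2.2 does not, so the rule is unclear. Vital signs (16.4), ECG (16.5) and the liver thresholds are already counted at any time post-baseline.

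**The case against.** The best reply is that little is at stake. The secondary endpoint is change from baseline, which is summarized for the quantitative laboratory results; a shift table is a supporting display. The SAP is to be read together with the protocol and nowhere withdraws the shifts. With about 22 participants, flagged listings let a reader trace each person. The protocol synopsis allows out-of-range safety results to be categorized, though only as an option. Results that the investigator judges clinically significant become adverse events and so reach the primary endpoint.

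Most of this stands and limits the severity. It does not remove the mismatch. Protocol 13.6.2 promises listings separately, so listings do not meet the shift commitment, and SAP 6.1 is where a change of display should appear.

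On PCS counts, no document requires any-time counting for hematology or chemistry, so by-time-point counting breaks no commitment. Nor does 16.2 itself invoke the record rule of 13.10. Both points stand: this half is a recommendation that rests on a reading of the SAP.

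There is also a fair objection to relying on a worst-value shift. It compares one baseline value with the worst of three or more. If each draw independently had a chance p of being out of range with no drug effect (an assumption), at least one of three would be out of range with probability 1 − (1 − p)³: 3% for p = 1%, 14% for p = 5%, 27% for p = 10%. There is no comparator to calibrate that rise.

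**Conclusion.** The plan should be changed, at the level of tables and wording. The missing shift display and the silence of SAP 6.1 are firm from the texts. Nine blood analytes have no planned abnormality count and no covered counterpart, which is 24% or 28% depending on how the white-cell differential is counted. The undercount of hematology PCS values is possible, not certain. It requires that SAP 13.10 govern those tables and that an abnormal unscheduled value exist. If it occurs, it can only lower the count.

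Three stronger readings are tempting, and the documents do not support them:
- A reader might infer that abnormal results go unreported. They do not: flagged listings, change summaries, adverse-event capture and any-time liver counts all remain.
- A reader might infer that the by-time-point tables are known to drop values or that they breach the protocol. Section 16.2 does not state the record rule, and the protocol asks only for a summary of PCS values.
- A reader might infer that the Days 18–25 gap loses planned data. No laboratory draw is scheduled then (Day 21 is a telephone call), and SAP 13.10 sends unscheduled visits outside every window to listings. What remains is a wording conflict with its statement that the windows leave no gap.

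**What to change.** - **Shifts.** Add low/normal/high shift tables from baseline to each scheduled post-baseline visit for hematology, chemistry and coagulation, and a categorical shift for urinalysis where a normal range exists. Give a shift to the worst post-baseline value as a supplement. Otherwise, declare and justify the omission in SAP 6.1.
- **PCS counts.** Count hematology and non-liver chemistry PCS values at any time post-baseline over all scheduled, unscheduled and early-termination records. Keep the by-time-point counts as a supplement, and align the title of Table 14.3.3.2.2 with the text.
- **Wording.** Reconcile the no-gap statement in SAP 13.10 with the uncovered Days 18–25 in SAP Table 1.

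If the database is already locked, the SAP Introduction requires the change and its justification to be described in the clinical study report.

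**Cost.** A few tables from data already collected; no change to visits, draws or the baseline definition. The tables will be more numerous and sparse at about 22 participants. Worst-value and any-time counts rise with the number of draws even without a drug effect, and a footnote should say so. Triglyceride shifts need a caution. Day −1 and Day 28 samples may be taken at any time of day and need not be fasted, while Day 7 and Day 14 samples precede the morning meal, so a shift may reflect meal state.
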